1.0 Background and Rationale

Schizophrenia is a chronic and disabling illness that is associated with impairments in independent living as well as social and vocational functioning¹. Schizophrenia also represents an important societal burden; only 10% of individuals maintain employment, translating into annual lost wages of nearly \$15 billion^{2,3}. Cognitive dysfunction is a core facet of schizophrenia, contributing to profound social and vocational difficulties⁴⁻⁶. Cognitive control (CC) is an important mental process that is reliably impaired in schizophrenia⁷⁻⁹.

CC facilitates flexible, goal-directed behavior through real time adjustments in perceptual selection, response biasing, and on-line maintenance of contextual information^{10,11}. CC deficits in schizophrenia are associated with poor treatment compliance, social and occupational dysfunction and decreased quality of life⁷⁻⁹. There are no effective treatments for CC impairment, due in large part to a **gap in knowledge** regarding the neural mechanisms of cognitive dysfunction in schizophrenia. In light of the significant functional disability and poor outcomes associated with impairment in CC there is a critical need for more effective therapeutic options for this important illness domain.

Recently research has suggested that CC is subserved by a functionally related neural circuit, referred to as the cognitive control network (CCN), that includes the left dorsolateral prefrontal cortex (LDLPFC), the left superior parietal cortex (LSPC), and the anterior cingulate cortex (ACC)^{10,12-14}. The ACC is a key node within the CCN and is believed to act as a network hub that strongly affects processing and connection efficiency¹⁵. Though previous work has demonstrated that disruption within the CCN, particularly decreased activity in the ACC, is associated with deficits in CC functioning^{12,16-18}, a clear understanding of the impact of ACC dysconnectivity remains elusive. There is a critical need to identify investigational techniques that clarify the neural underpinnings of CC impairment in schizophrenia, such as ACC dysfunction, and contribute to the development of effective treatments for this important cognitive deficit in schizophrenia.

Repetitive transcranial magnetic stimulation (rTMS) is a non-invasive neuromodulation technique that received FDA clearance for use in treatment resistant major depressive disorder in 2008 and has become commonly used in clinical practice¹⁹. rTMS utilizes the application of a repetitively pulsed magnetic field over the scalp to induce an electric field within a discrete area of the cerebral cortex. This electric field results in altered ion flow across the neuronal cellular membrane and ultimately changes in neuronal polarization. rTMS modulates cortical activation depending on the stimulation parameters used^{20,21}. Physiological studies have provided evidence that high-frequency (HF) rTMS produces an increase in local cortical excitability²⁰⁻²⁴. Studies have also demonstrated that rTMS may increase functional connectivity between separate but related cortical structures, utilizing high frequency stimulation²⁵⁻²⁸. Thus, rTMS allows investigators to manipulate focal brain activity in a target region and distal function in associated circuitry²⁵. The ability to affect activity downstream from the point of stimulation is important, as this enables investigators to modulate structures not directly accessible to rTMS, such as the ACC.

Work by our group and others have shown that rTMS is a viable option for investigating cognitive dysfunction in schizophrenia^{26,28-30}. We recently completed a pilot-study investigating the effects of HF rTMS, compared to sham stimulation, on cognitive dysfunction in an early phase psychosis (EPP) population. This study administered bilateral, sequential, double-blinded sham stimulation or HF (20 Hz) rTMS targeting the DLPFCs in twenty subjects with EPP. Ten

sessions of rTMS or sham were administered over the course of two-weeks. Our pilot-study demonstrated not only a beneficial effect of rTMS on cognition but also that the intervention is safe and well tolerated in subjects with EPP. There were no serious adverse events during the course of this study and there were no significant differences in adverse events between the rTMS and sham group.

In spite of existing work studying rTMS as a treatment modality in schizophrenia, there are no studies that have examined the effects of rTMS targeting superficial CCN structures (LDLPFC and LSPC) on ACC activity or CCN connectivity in schizophrenia. It is also important to note that the vast majority of studies using rTMS in schizophrenia have examined chronic populations where confounds associated with prolonged duration of illness may be present. EPP is a desirable population to study because these individuals tend to have fewer psychiatric and physical comorbidities and less antipsychotic drug exposure, all of which are factors that may confound investigations of new treatment interventions for this illness. In light of the significant unmet medical need associated with schizophrenia and the grave clinical effect of disrupted CC in the illness, rTMS modulating the ACC, and potentially CCN circuitry, represents an unexplored and novel potential treatment option.

The **goal of this project** is to utilize HF (20 Hz) rTMS, in conjunction with functional magnetic resonance imaging (fMRI), to provide evidence that rTMS targeting superficial CCN structures (LDLPFC and LSPC) modulates: 1) activation in the ACC during in-scanner CC task performance and 2) functional connectivity between the CCN structures during in-scanner CC task performance. This study will provide vital preliminary data on target engagement informing future clinical trials seeking to investigate rTMS as a novel treatment for CC impairment in schizophrenia. This study will also seek to refine the understanding of the brain circuitry that mediates the potential pro-CC effects of rTMS through the use of fMRI at baseline and following the course of rTMS administration.

2.0 Specific Aims and Hypothesis

The **first primary aim** is to define the impact of HF (20 Hz) rTMS targeting the LDLPFC and LSPC on ACC activation in individuals with schizophrenia during in-scanner CC task performance. We predict that HF rTMS targeting the LDLPFC and LSPC will result in increased functional activation in the ACC during performance of an in-scanner CC task. The **second primary aim** of this study is to define the impact of HF rTMS targeting the LDLPFC and LSPC on CCN functional connectivity (FC). We hypothesize that HF rTMS of the LDLPFC and LSPC will result in increased FC between the LDLPFC, LSPC, and ACC during performance of an in-scanner CC task. An **exploratory aim** of this study is to determine the effects of HF rTMS targeting the LDLPFC and LSPC will examine if HF rTMS targeting the LDLPFC and LSPC is associated with improved performance during on in-scanner CC task.

Primary Aim 2 Prediction

3.0 Study Design

This will be a single site pilot study. 20 subjects with EPP, defined as medical record documentation of the onset of clinically significant psychotic symptoms within the past 10 years, will be enrolled. Prior to randomization subjects will undergo fMRI during CC task (Stroop Color-Word paradigm) and resting-state paradigms. This baseline scan will also

include a high-resolution structural sequence for neuronavigation purposes. Then, on two separate days, each occurring one-week apart, subjects will receive one session of excitatory (20 Hz) rTMS targeting the LDLPFC and one session targeting the LSPC. The order of stimulation sites will be randomized and counter-balanced. Immediately following each session, subjects will undergo repeat fMRI during CC and RS paradigms. We will also examine the effect of rTMS on CC performance.

rTMS Set up and Administration

rTMS will be delivered using the Magventure MagPro X100 Magnetic Stimulator (Magventure Inc., Alpharetta, Georgia). Motor threshold (MT) will be determined using single pulse stimulation over the left primary motor cortex, assessed as the lowest intensity producing five visible movements of the right abductor pollicis brevis out of ten stimulations.

High Frequency rTMS

High frequency rTMS, or rTMS greater than 5 Hz, leads to faciliatory effects on brain excitability^{20-24,31}. Previous studies have demonstrated that administration of as little as a single train or a small number of trains are able to produce an immediate increase in cortical excitability²⁴. Additionally, earlier investigations have utilized high frequency rTMS in schizophrenia populations, demonstrating that the treatment is safe, well-tolerated and capable of altering cognitive performance^{30,32}. Our group has employed 20 Hz rTMS at 110% of motor threshold in a stimulation protocol in-line with the current proposal to improve cognitive function in an EPP cohort³⁰. High Frequency rTMS Protocol: Subjects will receive two sessions of HF rTMS, targeting the LDLPFC and LSPC, within the following stimulation parameters: 20 Hz, at 120% of MT, 60 trains (1.0 second per train), 20 pulses per train, inter-train interval of 20 seconds, for a total of 1200 pulses over 21 minutes. This stimulation protocol is within safety limits for rTMS^{21,33,34}.

Neuronavigation

Brainsight software (Rogue Research, Montreal Canada) will be used to reliably target the LDLPFC and LSPC for stimulation. First, the subject's individual anatomy will be registered stereotactically using the acquired structural MPRAGE brain image and fiduciary points on the scalp visible with a Polaris vicar camera (Brainsight software). We will use the centers of mass of the LDPLFC and LSPC (derived via Freesurfer parcellation; Destrieux Atlas³⁵; left/right combined) to identify the specific coordinates for stimulation. Stimulation sites will be marked on a swim cap worn by the subjects at each stimulation session, consistent with prior TMS studies²⁵.

Electrical field modeling

The processed structural image will be used to generate E-fields based on realistic conductor head models using SimNIBS (2.1 or latest version). SimNIBS includes volume conductor

modeling (following FreeSurfer segmentation), TMS coil specific magnetic dipole estimations, and finite element modeling of the electric field at each tetrahedral element of the subject's head mesh. In anticipation of actual TMS sessions with each patient, we will find the optimal TMS positioning to most strongly influence the LDLPFC and LSPC, which will be the target for neuronavigated rTMS delivery.

rTMS administration monitoring

All subjects will be instructed to wear earplugs during each rTMS session and will be monitored by medically trained research staff throughout the entirety of each rTMS session.

Duration of Treatment

Subjects will complete two stimulation sessions over two weeks, with one session occurring each week. Previous work has demonstrated that a single session of rTMS is sufficient to modulate target site functional activation as well as functional connectivity between the stimulation target and associated circuitry²⁵.

Sample Size

We plan to enroll 20 subjects and anticipate a 20% drop out rate, yielding 16 completers. This is consistent with our previous clinical trial efforts, including a study of adjunct rTMS in an EPP cohort^{30,36}. For all planned analyses, a total of 16 subjects in a counter-balanced design will result in 0.8 power to detect an assumed stimulation effect at medium effect size 0.6; using an alpha level of 0.05 and conservatively assumed a within-subject correlation of 0.5. As no CCN rTMS pilot data was available, this standardized effect size of 0.6 is considered a conservative estimate to detect significant results.

Clinical Research Site

The IU Psychotic Disorders Program (IUPDP), which is directed by [name] and is part of the IU Department of Psychiatry, is located in Indianapolis, Indiana. IUPDP research personnel will manage the day-to-day activities of conducting the trial, including subject recruitment, consenting and screening subjects, conducting study visits, and performing assessments. The IUPDP has 2 research psychiatrists, a fully dedicated study manager, a fully dedicated study coordinator, one dedicated subject recruiter, one dedicated research technician, and two raters (1 PhD, 1 Masters level) who have been trained and have extensive experience in conducting the assessments and cognitive tests used as outcome measures.

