13.0 Statistical Considerations

Analyses

Power Analyses

In terms of the power to detect a significant effect of HF rTMS on CC neurocircuitry or performance, there are no known calculations with EPP patients. However, previous investigations, including our own, used similar stimulation designs when investigating the effects of rTMS on overall cognitive performance. These studies demonstrated statistically significant results with sample sizes consistent with the current proposal³², and Cohen's effect sizes of d = 0.92 and 1.15, respectively^{30,32}. Though these previous studies examined different cognitive constructs than the CC task in this current protocol, these studies do provide evidence that a similar stimulation design is sufficient to elicit a biologic response and assumedly appropriate for investigating the effects of rTMS on CC.

We believe that for the purpose of this pilot study, we can demonstrate significant results with a sample size of 16 (eight per group). This accounts for the effect size estimate derived from the literature, d = 1.1, and the estimation of power to detect an effect at .75, utilizing a one-sided independent test and significance levels of 0.05.

Statistical Analyses

Preliminary analyses will consist of descriptive statistics for all outcome variables, including summary statistics, graphical displays of distributions, and spaghetti plots of individual data over time to detect possible data errors. Demographic and clinical characteristics at baseline will be examined using parametric or nonparametric test statistics as appropriate. Any demographic variables that show significant differences will be added to the final models as covariates in order to ensure that the observed stimulation effects are not spurious or due to demographic confounds.

To minimize the potential for Type II error, all treatment comparisons will be evaluated based on a one-sided significance level of 0.05. To compare overall effect of stimulation over time for the two groups, a set of multivariate repeat measures analysis of variance (ANOVA) will be utilized, with stimulation as the between-group factor and time as the within-subject factor.

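### Section 13.0's between-group model does not fit a design in which every subject receives both active sites; an equal rise at both sites shows only in the time term, which cannot attribute it to rTMS

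*Combined protocol and SAP*

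**What the plan says.** Section 2.0 states the first primary prediction: "We predict that HF rTMS targeting the LDLPFC and LSPC will result in increased functional activation in the ACC during performance". The second predicts a rise in connectivity among the three network regions. Both concern an increase after stimulation, and neither predicts that one site does better than the other.

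Section 3.0 sets the sequence. "Prior to randomization subjects will undergo fMRI during CC task (Stroop Color-Word paradigm) and resting-state paradigms". Each subject then has one active session at each site, a week apart, with a scan after each. "The order of stimulation sites will be randomized and counter-balanced". Attachment 1 agrees: baseline MRI at Visit 1, randomisation of order at Visit 2, post-stimulation MRI at Visits 2 and 3. No sham or unstimulated repeat scan is scheduled; sham appears only in the account of the earlier pilot in Section 1.0.

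The two statistical passages describe different analyses. Section 3.0 (Sample Size) says "For all planned analyses, a total of 16 subjects in a counter-balanced design will result in 0.8 power to detect an assumed stimulation effect", with effect size 0.6 and within-subject correlation 0.5. Section 13.0 says "we can demonstrate significant results with a sample size of 16 (eight per group"), from d = 1.1, power 0.75 and a one-sided independent test. Its analysis is introduced with "To compare overall effect of stimulation over time for the two groups", by repeated-measures ANOVA "with stimulation as the between-group factor and time as the within-subject factor".

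**The concern.** Stimulation does not vary between subjects here. The only groups that randomisation creates are the two site orders, and both orders receive both active sites. An effect common to the two sites is therefore the same in each group and drops out of any comparison between them. What remains is change over time from a scan that is first for everyone, and that change contains whatever else happens between a first scan and later ones: task practice, scanner habituation, elapsed time.

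Section 1.0 says what the result is for: "This study will provide vital preliminary data on target engagement informing future clinical trials". If the group comparison is run as written, it has no power for a rise common to both sites. If post-minus-baseline change is used instead, a rise could be a repeat-scan effect reported as target engagement, and a null could be habituation hiding a real effect.

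**Working it through.** **Inputs.** From Section 3.0: 16 completers, effect size 0.6, within-subject correlation 0.5, alpha 0.05. From Section 13.0: eight per group, d = 1.1, one-sided 0.05. Assumed: SD 1 at each scan, equal correlation between scans, eight subjects per order. Drift sizes are assumptions throughout.

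**1. The plan's own power figures.**
- Section 3.0 (0.80). One paired contrast has standardised size 0.6/√(2(1−0.5)) = 0.6. With n = 16, the noncentral t gives 0.740 one-sided and 0.612 two-sided (normal approximation 0.775 and 0.670). A contrast the section does not name, the mean of both post scans minus baseline, has SD √(1.5 × 0.5) = 0.866 and gives 0.791 by two-sided normal approximation (0.736 by t).
- Section 13.0 (0.75). d = 1.1 with eight per group, one-sided, gives 0.711 by normal approximation and 0.673 by t.

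The two statements rest on different tests and different effect sizes. The point below does not depend on either figure.

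**2. What the design can estimate.** Take 16 subject terms, 2 scan-position terms (scans 2 and 3) and 2 site terms: 20 columns. Every post scan belongs to exactly one scan position and one site, so the two site columns add up to the same vector as the two position columns. The rank is 19. Each site's effect, and their sum, are not estimable once scan position is free. LDLPFC minus LSPC and scan 3 minus scan 2 are. No drift size enters this step.

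**3. Section 13.0's terms, for a common 0.6 SD increase and no drift.** The changes from baseline at scans 2 and 3 each have variance 2(1−0.5) = 1 and covariance 0.5.
- Group-by-time: the two orders have the same mean changes, so noncentrality is 0 and rejection equals alpha. Simulation gives 4.9% to 5.1%.
- Group main effect, one-sided: 4.8% by simulation. A one-sided independent test of mean post-minus-baseline change between orders: 5.1%.
- Time, F(2,13): noncentrality 16 × 0.6² × 2/1.5 = 7.68, power 0.589.

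**4. The same terms, with no rTMS effect and an equal shift at both later scans (assumed).**
- Group-by-time at +0.3 SD: 5%.
- Time at +0.2 SD: noncentrality 16 × 0.2² × 2/1.5 = 0.853, rejection 10%. At +0.3 SD: 1.92, rejection 18%.

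**5. Both directions of drift, for a one-sided one-site post-minus-baseline t-test.** Section 13.0 does not name this test; it serves only as an illustration. The change has SD 1.00, with 15 df, critical value 1.753 and noncentrality 4 × (effect + drift).

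| Assumed drift (SD) | Rejection, no rTMS effect | Power, true 0.6 SD |
|---|---|---|
| −0.3 | 0.3% | 31% |
| −0.2 | 0.8% | 45% |
| −0.1 | 2.1% | 60% |
| 0 | 5% | 74% |
| +0.1 | 10% | – |
| +0.2 | 19% | – |
| +0.3 | 31% | – |

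Power under upward drift is left blank because rejection there mixes effect and drift.

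**6. Precision of the randomised site contrast.** Residual variance per scan is 1 − 0.5 = 0.5, so SE = √(2 × 0.5/16) = 0.25. A model on all three scans has 48 observations less 19 parameters (16 subject, 2 condition, 1 session), hence 29 df: half-width 2.045 × 0.25 = 0.51 SD. A two-scan crossover analysis has 14 df: 2.145 × 0.25 = 0.54 SD. Two-sided power is 64% or 61% for a 0.6 SD site difference, and 21% or 20% for 0.3 SD.

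**The case against.** Five points deserve weight.

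*The model includes time.* A reader might infer that Section 13.0 cannot test the prediction at all. The documents do not support that: the model has a within-subject time factor, and if baseline is one of its levels that term responds to a common increase. The failure to detect is confined to the group and group-by-time terms. The time term's limit is attribution.

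*Section 13.0 can be read loosely.* It defines neither the groups nor stimulation. They may mean the two site conditions, mislabelled as between-group, and Section 3.0 already contemplates a within-subject analysis. This stands as a reason to reconcile the two passages. Neither reading supplies a control for scan order.

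*Practice is addressed.* Section 6.0 provides alternate task versions and practice before scans. These may reduce task learning; they do not deal with scanner habituation or elapsed time.

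*Drift is hypothetical.* Correct. The documents give no size or direction, so they do not support saying that the trial will produce false positives. Downward drift makes the test conservative and costs power instead.

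*It is a pilot.* An uncontrolled before-and-after pilot is a legitimate choice, and nothing here requires a sham arm. But Section 1.0 also sets the goal of providing evidence that rTMS modulates these measures, which goes further than an uncontrolled change can.

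**Conclusion.** The concern holds for the analysis plan and the claim, not as an objection to running this design. Section 13.0's between-group model and its power paragraph do not match Section 3.0 and Attachment 1, and they conflict with the counter-balanced, within-subject basis of the sample size. For an equal 0.6 SD increase at both sites, the group and group-by-time terms reject at about 5%. The time term rejects about 59% of the time but cannot separate rTMS from scan order.

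The confounding follows from the design alone. The 5% and 59% rest on n = 16, correlation 0.5, unit SD and equal correlation. The illustrative ranges (10% to 31% false positives for upward drift; power falling from 74% to between 60% and 31% for downward drift) rest on assumed shifts of 0.1 to 0.3 SD. A reader might also infer that the 0.80 in Section 3.0 is simply wrong. That goes too far, since one unstated contrast gives 0.791; the finding is that the contrast needs naming.

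**What to change.** Keep the visits and scans; change the model and the wording.

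1. **Section 13.0, model.** For each outcome, replace the between-group model with a within-subject one: subject, condition (baseline, post-LDLPFC, post-LSPC), and session coded −0.5/+0.5 at the two post scans and 0 at baseline, with a stated covariance structure. Report, with 95% CIs, post-minus-baseline change for each site and the period-adjusted LDLPFC-minus-LSPC contrast. Test the site contrast two-sided, since Section 2.0 predicts no direction between sites. Reconcile the power statements in Sections 3.0 and 13.0 and restate them for these contrasts.
2. **Sections 2.0 and 13.0, claim.** State that post-minus-baseline is an uncontrolled change that cannot by itself be attributed to rTMS. State that the randomised site contrast addresses site difference only and assumes no differential carryover. Report the comparison between orders at Visit 2 as a carryover-free sensitivity check.
3. **Period effect.** Report session 2 minus session 1 with its CI, descriptively. It mixes drift with carryover, and a value near zero does not exclude a shift between scans 1 and 2, so do not use it to correct the post-minus-baseline change.

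**Cost.** Document and analysis work only. The headline claim becomes weaker. The site contrast is imprecise (±0.51 to ±0.54 SD, as shown above). The Visit 2 check is more so: taken on change from baseline, its SE is √(1/8 + 1/8) = 0.5, or ±2.145 × 0.5 = ±1.07 SD.

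### Does the phrase about combining left and right regions move stimulation away from the left-sided sites named in the aims?

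*Combined protocol and SAP*

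**What the plan says.** Section 1.0 defines both abbreviations as left-hemisphere structures: "the left dorsolateral prefrontal cortex (LDLPFC), the left superior parietal cortex (LSPC". The first aim in Section 2.0 is to "define the impact of HF (20 Hz) rTMS targeting the LDLPFC and LSPC on ACC activation". The design paragraph of Section 3.0 states that "subjects will receive one session of excitatory (20 Hz) rTMS targeting the LDLPFC and one session targeting the LSPC", and the Study Procedures Table (Attachment 1) lists the same two sites for stimulation at Visits 2 and 3.

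Two subsections of Section 3.0 then describe targeting. Neuronavigation begins the rule with "We will use the centers of mass of the LDPLFC and LSPC" and adds, in a parenthesis about the FreeSurfer/Destrieux derivation, that the parcellation is "left/right combined) to identify the specific coordinates for stimulation". The sentence after it says that "Stimulation sites will be marked on a swim cap worn by the subjects at each stimulation session". Electrical field modeling says that "we will find the optimal TMS positioning to most strongly influence the LDLPFC and LSPC, which will be the target for neuronavigated rTMS delivery".

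**The concern.** A left-sided region has no right-hand part to combine. Taken literally, the parenthesis asks for one centre of mass over a left region and its mirror image, and that point falls close to the midline, outside the left region. The electric-field subsection adds to the doubt. It also says what the target is, and it uses a different quantity: the position with the strongest modelled effect, not a geometric centre. Neither statement refers to the other, and the text does not say which site is marked on the cap.

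The stake would be real if the literal reading were followed. Each subject has one session per site, there is no sham session, and randomization concerns only the order of the sites. The conclusions therefore rest on which cortex was stimulated. With 16 expected completers, inconsistent targeting would add variability that the study could not easily absorb, and a null result would be hard to tell from stimulation in the wrong place.

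**Working it through.** There is no stated figure to reproduce, because targeting does not enter the sample size, alpha, power or effect size. The check is a comparison of the passages, plus one piece of geometry.

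**Which hemisphere does each statement name?**

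| Place | Site named |
|---|---|
| 1.0 Background (definition) | left DLPFC, left SPC |
| 2.0 Aims | LDLPFC, LSPC |
| 3.0 design paragraph | LDLPFC, LSPC |
| 3.0 Neuronavigation, main clause | LDLPFC, LSPC |
| 3.0 Neuronavigation, parenthesis | left and right combined |
| 3.0 Electrical field modeling | LDLPFC, LSPC |
| Attachment 1, stimulation row | LDLPFC or LSPC |

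One parenthesis stands against every other statement, including the main clause of its own sentence.

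**What does the literal reading imply?** Put the left region's centre at −L and its mirror image at +L, with right-to-left volume ratio r. The combined centre of mass is

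x = L(r − 1)/(r + 1),

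and its distance from the left centre is x + L.

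- r = 1: x = 0, so the distance is L.
- r = 0.8, L = 20 mm: x = 20 × (−0.2/1.8) = −2.2 mm; distance 17.8 mm.
- r = 1.25, L = 40 mm: x = 40 × (0.25/2.25) = 4.4 mm; distance 44.4 mm.

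Both L (20 to 40 mm) and r (0.8 to 1.25) are assumptions, since the documents give no coordinates or volumes. For equal volumes the answer is the assumed L handed back. The geometry shows that the literal reading gives a near-midline point. It says nothing about whether anyone would use that reading. Such a point is not the centre of mass of the LDLPFC or the LSPC, so the literal reading contradicts the clause it sits in.

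**Do the two target statements conflict on region?** One gives an anatomical reference for each region. The other gives a position chosen for its modelled effect on the same two regions. They can be read as two steps, locating the cortical region and then placing the coil to reach it, although the plan does not say so. The resulting points may differ, but both statements are tied to the left-sided regions in the aims.

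**Would the comparison of sites be lost?** Section 2.0 states no hypothesis that the two sites differ. Even on the literal reading, the displacement runs along the left-right axis only. The calculation does not show that a prefrontal and a parietal point would become indistinguishable.

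**The case for a change.** The strongest reply is that the sentence fixing stimulation coordinates should not need interpretation. Section 1.0 presents the study as preliminary evidence of target engagement, so the site is the experimental variable. The pilot described there stimulated the DLPFC on both sides, which makes inherited wording plausible, but a leftover in that sentence is still an error. An operator who noticed a midline coordinate would find no written rule for what to use instead. An outside reader also cannot tell from the text how the centre of mass and the modelled position fit together, or which of them is marked on the cap.

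Part of this stands. The parenthesis is unexplained and does not fit left-only targets, and the link between the two targeting statements is missing. The step from there to harm does not stand. This is a single-site study, and nothing in the documents suggests that operators would work to different rules. The text leaves open which site is marked on the cap, so the marking sentence cannot be used as evidence that the centre of mass prevails. Recording delivered coordinates for every session may be useful, but the need for it does not follow from this ambiguity.

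**Conclusion.** No change to the plan follows. The discrepancy is a clerical slip in one parenthesis together with a linking detail that the study team can supply. The two targeting passages need to be reconciled in wording, and this review takes no position on which targeting quantity should govern. Reconciling them would not alter which regions are stimulated, which outcomes are measured or what the trial can conclude.

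The size on the statistical side is nil: the 16 completers, the assumed effect size and the alpha are untouched. No displacement in millimetres can be derived from the documents. The conclusion assumes that the team reads the parenthesis in line with the left-sided regions named in the same sentence and throughout the protocol. If the literal midline reading had actually been used at the sessions, the conclusion would be different, but nothing in the documents points to that.
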